3 STUDY OUTCOMES

Primary outcome measure is time to heal in patients treated with epidermal grafting and SOC vs. SOC alone (**Group 1A** versus **Group 2A** at 6 weeks; and **Group 1A** versus **Group 2B** at 12 weeks).

Secondary outcomes include:

1. Percentage of wounds closed at 6 and 12 weeks.
2. Correlation between protease activity and healing at 4 and 8 weeks.
3. Incidence of adverse events at 12 weeks.
4. Pain reduction between baseline and 12 weeks.
5. Cost-effectiveness (see Appendix 19.4)
6. Cost-benefit (see Appendix 19.4)

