6.3 TREATMENT PHASE

TREATMENT VISIT 1 (TV1) – PRIOR TO RANDOMIZATION

The following procedures must be performed:

- Pain assessment

CELLUTOME™ IN VENOUS LEG

- Assess effectiveness of compression bandaging
- Check for any changes in the subject's health and update the Medical History with any changes
- Assess concomitant medications
- Assessment of study ulcer
- Check for signs of clinical infection of the study ulcer.
- Clean the study ulcer with saline.
- Digital photo of the study ulcer
- Debridement, if required to remove non-viable tissue
- If the subject is eligible, perform the following procedures (TV1) immediately.
- If the subject is not eligible, discharge the subject from the study as a screen failure.

TREATMENT VISIT (TV1) – RANDOMIZATION

- Randomize the subject
- Perform swab on study ulcer
- If randomized to the epidermal grafting arm: Harvest epidermal grafts using the CelluTome™ device then apply the grafts to the wound bed. (Procedure detailed in Appendix 10).
- If randomized to standard of care apply provided foam to the ulcer.
- Apply multi-layer compression therapy
- Complete Quality of Life, PBI-P, and Time trade off questionnaires (see Appendices 19.5, 19.6, and 19.2)
- Schedule the next study visit one week later

TREATMENT PHASE VISITS TV2-4, 6, 8, 10, 12

The following procedures must be performed:

- Pain assessment
- Assess compression bandaging
- Assess concomitant medications
- Check for any changes in the subject's health and update the Adverse Events or Serious Adverse Events pages with any events
- Study ulcer closure assessment will be determined by a blinded observer
 - If the study ulcer is 100% re-epithelialized, the subject will be scheduled for a Pre-Healing Confirmation Visit (HCV) one week later
 - If the study ulcer is healed, no other study procedures need to be completed at this visit
- Check for signs of clinical infection. If clinical diagnosis of infection has been made, then the subject can be treated with topical antimicrobials or oral antibiotics, but topical antibiotics CANNOT be used on the study ulcer. During the time that an infection is being treated,

CELLUTOME™ IN VENOUS LEG

treatment with the IP will be stopped.

- Digital photo of the study ulcer
- Apply Prisma™ or approved antimicrobial dressing at TV4, TV8 for both **Groups 1A/2A,2B**; and at TV10 for **Group 2C**.
- Apply provided foam and multi-layer compression bandaging therapy.
- The next visit will be scheduled for one week.

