8.7.3 INVESTIGATOR ASSESSMENT OF STUDY ULCER CLOSURE

“**Complete healing**” of the study ulcer is defined as 100% re-epithelialization without drainage. At each visit, the investigator will assess the wound by answering the following questions:

- Study ulcer 100% re-epithelialized?
- Drainage is absent?

Both questions must be answered “yes” for the study ulcer to be considering having reached “complete closure”.

The date of complete healing is defined as the date of the first assessment of 100% re-epithelialization.

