9.6 INTERIM ANALYSIS

One interim safety and efficacy analysis will be performed when approximately 110 subjects have been enrolled (approximately 50% of subjects). The total number of AEs and SAEs will be calculated, and the proportion of healed wounds tabulated for all groups (at 12 weeks). New sample size calculations will be performed based on the proportion of healed wound data (time to heal). No statistical analysis will be conducted.

TRIAL STOPPING RULES

The Medical Monitor may unblind, or appoint an independent assessor to unblind interim data analyses to determine whether the study should be stopped if any of the following occur:

- If the primary outcome likely has reached statistical significance and there is agreement to analyze the secondary outcomes regardless of whether they are likely to achieve statistical significance or not.
- If the primary outcome has likely not reached statistical significance and based on futility boundary analysis, the numbers of additional subjects needed to reach significance based on the rate data are too high to realistically extend the trial.
- $\geq 25\%$ of ulcers have deteriorated (meaning an increase in area from baseline to 12 weeks).
- A significant proportion of patients ($> 25\%$) in either group continue to experience infections despite Prisma/antimicrobial treatment or other measures
- Excessive non-planned withdrawal of subjects

List of variables for interim analysis

- Site ID
- Subject ID
- Treatment assignment
- Gender
- Pain score at baseline and 12 weeks
- Wound healed (Y/N) by 12 weeks (after 12 weeks have elapsed from date of randomization)
- When wound healed (days from randomization)
- Ulcer area at baseline and 6/12 weeks
- AEs (by category; have separate category for infected wounds) and SAEs at 12 weeks (count by subject, and description/category where applicable)
- Withdrawn subjects or subjects that have been lost to follow-up (count and by assignment with reason where applicable)
- Number of subjects in **Groups 2B and 2C**.

PATIENT POPULATIONS

The populations defined for the final analysis will include the intent-to-treat (ITT), per protocol (PP), and safety populations.

INTENT-TO-TREAT POPULATION

The ITT population will be analyzed for primary and secondary endpoints up to 12 weeks; however, Index Ulcers that have been healed are still subject to confirmed wound closure for 2 weeks later (up to 14 weeks for ulcers initially healed in the 12th week).

PRE PROTOCOL POPULATION

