- Reduction in pain score (baseline – Week 12) will be analyzed by paired t test if the dependent variable data are not grossly non-normal or the Mann-Whitney test if they are grossly non-normal (unadjusted).

To create the flow chart, the following numbers will be required for each group: eligible (n), screened (n), screen failure (n, with categorical reasons), randomized (n), completed 12 weeks study (n), withdrawals or lost to follow-up after randomization (n, with categorical reasons).

These variables are required for the final analysis:

- Site ID (alphanumeric)
- Patient ID (alphanumeric)
- Year enrolled (numeric; date, year only)
- Group assignment (nominal factor, [1A, 2A, 2B, 2C]; note: subjects in 2A can also have 2B or 2C assignments as well)
- Lost to follow up (binomial factor [1,0; 1 = yes]; estimated date lost to follow-up; associated patient ID; categorical reason for lost to follow-up)
- Death during study (binomial factor [1,0; 1 = yes]; estimated date when death occurred)
- Gender (nominal factor [1, 0; male = 1])
- Subject age at S1 (continuous variable with breakpoint at > 90 years if > 90)
- Ethnicity/race (multinomial factor)
- Smoking status at S1 (ordinal factor: [1, 2, 3; never, ever, current])
- Wound count (Poisson distribution variable; count of VLU at patient level at randomization)
- Index Ulcer location (multinomial factor)
- Prior VLU at S1 (binomial factor [1,0; 1 = yes])
- Wound age at S1 (continuous variable, days; S1)
- Pain score (continuous variable, 0-10, TV1 and 13)
- VCS score at S1 (continuous variable, 0-24)
- BMI at S1 (continuous variable)
- Diabetes at S1 (nominal factor [1, 0; yes = 1])
- Subject on pain medication at S1 (nominal factor [1, 0; yes = 1])
- Wound area (continuous variable, cm²; weekly, weeks TV1-13)
- Wound depth (continuous variable, cm; weekly, weeks TV1-13)
- Outcome healed at 12 weeks (binomial factor, [1,0; 1 = yes])
- Time to heal (continuous variable, 0-84, days after randomization for healed wounds)
- Initial wound healed within 12 weeks and confirmed closed about 2 weeks later (binomial, [1,0; 1 = yes])
- Ulcer recurrence by 12 weeks (binomial factor, [1,0; 1 = yes]; estimated days after randomization when event occurred)
- Infection episode (Poisson variable, weeks TV1-13)
- AE (Poisson distribution variable, count at patient level; date of onset)

CELLUTOME™ IN VENOUS LEG

- TEAE (Poisson distribution variable, count at patient level for each of 4 categories; date of onset)

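### Complete healing requires re-epithelialisation and no drainage, but its date is set by re-epithelialisation alone, so some primary events can be dated before the definition is met

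*Combined protocol and SAP*

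**What the plan says.** Section 8.7.3 states that complete healing "is defined as 100% re-epithelialization without drainage". The investigator answers one question on each condition at every visit, and both answers must be yes. The section closes with the dating rule: "The date of complete healing is defined as the date of the first assessment of 100% re-epithelialization". Drainage does not appear in that sentence.

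The other places that touch on closure are these:

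- Section 3: "Primary outcome measure is time to heal in patients treated with epidermal grafting and SOC vs. SOC alone". Section 9.2 (H1) tests this by log-rank, followed by Cox regression if a result is significant, for the 6-week and 12-week comparisons.
- Section 6.3, visit lists before TV13: "If the study ulcer is 100% re-epithelialized, the subject will be scheduled for a Pre-Healing Confirmation Visit (HCV) one week later". Drainage is not part of this trigger.
- Section 9.6, under the intent-to-treat population: "Index Ulcers that have been healed are still subject to confirmed wound closure for 2 weeks later". It allows this to run to week 14 for ulcers first healed in week 12, but does not say which visit supplies the event date.
- Section 9.7, list of variables: "Time to heal (continuous variable, 0-84, days after randomization for healed wounds". This restricts the variable to healed wounds but gives no dating rule. Healed status at 12 weeks and later confirmed closure are listed as separate variables.

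**The concern.** The event and its date follow different rules within one short section. An ulcer that is re-epithelialised but still draining at one visit, and dry at a later one, is completely healed only at the later visit, yet the written rule dates it to the earlier one.

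This matters because the date is the primary variable. The rule also decides which side of the 6- or 12-week boundary an event falls on. An ulcer re-epithelialised but draining at week 12, and dry only at a later confirmation visit, carries a date inside the window although the definition was met outside it. For that subject, the time-to-heal analysis (H1) and the proportion healed at 12 weeks (H2) could give different answers. The analyst would have to choose a rule after seeing data, in an open-label trial.

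**Working it through.** **Step 1. Size of the dating error for one ulcer.** Let visit k be the first re-epithelialised visit and k+m the first visit at which drainage is also absent.

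- Error = m visits, nominally 7m days. If m = 0, the error is zero.
- For m = 1, the nominal error is 7/84 = 1/12 of the 12-week horizon, or 7/42 = 1/6 of the 6-week horizon.
- Section 6.1 times each visit from TV1 with a ±2-day window. TV2 can fall on day 7 + 2 = 9 and TV3 on day 14 − 2 = 12, a gap of 3 days. At the other extreme the gap is (14 + 2) − (7 − 2) = 11 days. Seven days is therefore a nominal value, not a minimum.

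**Step 2. The plan's own power figure.** Inputs from section 9.3: 113 control and 112 treated subjects, hazard ratio (HR) 1.74, control proportion healed 0.5, 12 weeks with no accrual period, weekly dropout 0.033 (control) and 0.0083 (treatment), two-sided alpha 0.05. Exponential healing is assumed.

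- Control hazard = −ln(0.5)/12 = 0.0578 per week; treatment hazard = 1.74 × 0.0578 = 0.1005 per week.
- Expected events: 47.6 + 75.4 = 123.0. This is a model output; the plan states no event count.
- Lakatos-type log-rank power: 85.7%.
- Schoenfeld: Φ(√123.0 × ln(1.74)/2 − 1.96) = 86.7%.
- Freedman: Φ(√123.0 × 0.74/2.74 − 1.96) = 85.0%.

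All three lie within 2 points of the stated 86.1%. The sample size arithmetic is not in question here.

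**Step 3. Sensitivity to the dating rule.** The documents give neither the share of ulcers still draining at the first re-epithelialised visit nor the duration, so both are assumed. Trials were simulated with the section 9.3 inputs and weekly visits, 3,000 per cell. Rule A counts and dates the event at first re-epithelialisation. Rule B does so at the first visit with both conditions met.

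| Draining, control / graft | Lag (weeks) | Power A / B | HR A / B | Mean events A / B |
|---|---|---|---|---|
| 0% / 0% | – | 86.0% / 85.4% | 1.772 / 1.765 | 121.8 / 121.8 |
| 10% / 10% | 1 | 84.8% / 85.2% | 1.762 / 1.764 | 122.0 / 121.1 |
| 10% / 10% | 2 | 86.8% / 85.1% | 1.768 / 1.774 | 122.1 / 120.4 |
| 30% / 30% | 1 | 85.2% / 84.1% | 1.765 / 1.756 | 122.1 / 119.7 |
| 30% / 30% | 2 | 84.9% / 83.9% | 1.767 / 1.750 | 122.0 / 117.6 |
| 10% / 30% | 1 | 85.2% / 81.0% | 1.762 / 1.707 | 121.8 / 120.7 |
| 10% / 30% | 2 | 84.9% / 76.9% | 1.765 / 1.665 | 121.8 / 118.8 |
| 0% / 30% | 1 | 87.0% / 79.6% | 1.771 / 1.690 | 121.9 / 120.7 |
| 0% / 30% | 2 | 86.2% / 71.1% | 1.765 / 1.616 | 121.8 / 119.7 |

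The two rules were simulated independently. The standard error of one power estimate near 85% is √(0.85 × 0.15/3000) = 0.65 points, and of a difference about 0.65 × √2 = 0.9 points. The first row, where the rules are identical, differs by 0.6 points from chance alone. The 0–2 point differences under equal draining are therefore little more than simulation noise; those under unequal draining are not.

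Limits: the move of control subjects to Group 2C is not modelled, only the 12-week comparison was run, and unequal draining was run only in the direction of more drainage in the graft arm. Rule A also counts ulcers that dry only after the window, so the comparison includes the boundary cases.

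**The case against.** The best defence is that the sentence is a back-dating convention. Sections 6.3 and 9.6 call for a later confirmation, so the plan needs to say whether the event takes the first closed visit or the confirming one. The word for the first assessment plausibly does that, with drainage left out by loose drafting. This is a fair guess at the intention, but the sentence names only re-epithelialisation. Taken literally, it would also date an ulcer that closed, reopened and closed again to its first closure.

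The defence is stronger on consequences. A reader might infer that an ulcer which drains throughout acquires a healing date and enters the analysis as an event, or that H1 and H2 conflict generally. The documents do not support that: section 8.7.3 makes status depend on both answers, and section 9.7 limits time to heal to healed wounds. An ulcer that never stops draining is most naturally censored. What survives is the shift in date and the boundary case at 6 or 12 weeks.

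A reader might also want a count of misdated events. None can be given, because no document states how often drainage outlasts re-epithelialisation. Nor do the documents give any reason to expect a difference between arms, so the larger shifts in the table illustrate sensitivity and are not predictions.

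**Conclusion.** The point holds as an inconsistency in the dating of the primary event. Section 8.7.3 is the only dating rule, and it omits one of the two conditions in the definition it serves. Early dating is possible only for ulcers still draining at the first re-epithelialised visit, by about 7 days per weekly visit; it would be wrong to say that events in general are dated early.

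Under assumed equal draining (10–30%, lag 1–2 weeks) the effect on power is about 0–2 points. Under assumed unequal draining (30% in the graft arm against 0–10% in control), the HR moves from about 1.76–1.77 under the written rule to 1.62–1.71 under the two-condition rule, and power from about 85–87% to 71–81%. All of this rests on assumed shares and lags. The reason to act is that the primary event date should be unambiguous before data are seen.

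**What to change.** In section 8.7.3, define the date of complete healing as the first visit at which both questions are answered yes. If confirmation is part of the endpoint, make it the first such visit of a closure that is later confirmed. Use that visit for both the time-to-heal event (H1) and the healed proportion (H2), and repeat the rule beside the variable in section 9.7.

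Align these in the same edit:

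- The section 6.3 trigger for the confirmation visit, which rests on re-epithelialisation alone.
- The confirmation interval, which is one week in section 6.3 and about two weeks in sections 9.6 and 9.7.
- The assessor of closure, who is the investigator in section 8.7.3 and a blinded observer in section 6.3.

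The core change is one sentence and needs no new data, since both answers are already recorded at each visit. The alignment adds short edits in three sections.

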8.8 STUDY ULCER PHOTOGRAPHS

The study ulcer will be digitally photographed according to the schedules in this protocol. The digital photographic measurements will be used for surface area measurements to determine eligibility.

8.9 RANDOMIZATION

Subjects who are eligible to participate in the trial will be randomized by computer to one treatment group at the TV1 visit.

8.10 ASSESSMENT OF MULTI-LAYER COMPRESSION THERAPY

The following measurements will be taken to assess the performance of the compression bandaging during the Screening and Treatment Phase visits and at selected Follow-up visits:

1. Whether the bandage was in place at each visit (Yes/No).
2. If the bandage was not in place, the date it was removed and the reason for removal (slippage, strikethrough or other).
3. If the bandage is in place but needs to be changed at an unscheduled visit, the reason for removal/change must be recorded from the following:
 - a. Maximum wear time
 - b. Subject withdrawn
 - c. Adverse event
 - d. Slippage
 - e. Primary dressing change needed
 - f. Soiled
 - g. Subject request
 - h. Other

9.1 BRIEF TRIAL DESCRIPTION

THIS TRIAL IS A RANDOMIZED CONTROLLED TRIAL (RCT) IN WHICH SUBJECTS WITH VENOUS LEG ULCERS (VLUS) WILL BE RANDOMIZED 1:1 TO A MAXIMUM OF 3 TREATMENTS OF CELLUTOME™ 4 WEEKS (GROUP 1A) OR STANDARD OF CARE (SOC; GROUP 2A) AND FOLLOWED FOR 12 WEEKS. PRIMARY ENDPOINT IS TIME TO HEAL WITHIN 6 AND 12 WEEKS. IF WOUNDS IN GROUP 2A HAVE NOT BEEN REDUCED IN AREA BY AT LEAST 40% BY 6 WEEKS, PATIENTS WILL BE ALLOWED TO RECEIVE CELLUTOME™ TREATMENT (GROUP 2C; 2 TREATMENTS WITHIN THE REMAINING 6 WEEKS). THE REMAINDER OF THE SOC PATIENTS WILL BECOME GROUP 2B.

9.1.1 GENERAL

Descriptive statistical methods will be used to summarize the data from this study with hypothesis testing performed for primary and secondary endpoints. These include number of subjects (n), mean, median, standard deviation, minimum, and maximum for continuous data, and frequencies and percentages for categorical data. All data collected during the study will be reported and analyzed.

Unless specified otherwise, all statistical testing will be two-sided and performed using a significance (alpha) level of 0.05.

All statistical analyses will be conducted using PASW 19.

9.2 RESEARCH HYPOTHESES

Primary endpoints

H1: Time to heal

Time to heal after 12 weeks of CelluTome™ + SOC (**Group 1A**; maximum of 3 CelluTome™ applications) versus 12 weeks of SOC (**Group 2B**) will be equal for both groups or time to heal after 6 weeks of CelluTome™ + SOC (**Group 1A**; maximum of 2 CelluTome™ applications) versus 6 weeks of SOC (**Group 2A**) will be equal for both groups. Formally, $H_0: T_1 - T_2 = 0$; $H_A: T_1 - T_2 = D_1 \neq 0$, where T_1 is the time to heal for **Group 1A**, T_2 is the time to heal for **Group 2A or 2B** depending whether T_2 is 12 or 6 weeks, D_1 is the difference ($T_1 - T_2$) assuming the alternative hypothesis, and statistical test used is log rank applied to a Kaplan-Meier analysis. If either result is statistically significant, results will be adjusted using Cox regression and appropriate covariates.

Secondary endpoints

H2: Proportion of wounds healed

The proportion of wounds healed at 12 weeks after 12 weeks of CelluTome™ + SOC (**Group 1A**; maximum of 3 CelluTome™ applications) versus 12 weeks of SOC (**Group 2B**) will be equal for both groups. Formally, $H_0: P_1 - P_2 = 0$; $H_A: P_1 - P_2 = D_1 \neq 0$, where P_1 is the proportion of wounds healed for **Group 1A**, P_2 is the proportion of wounds healed for **Group 2B**, D_1 is the difference ($P_1 - P_2$) assuming the alternative hypothesis, and statistical test used is chi square.

H3: Incidence of Adverse Events (AEs)

The incidence of adverse events (AEs) by 12 weeks after 12 weeks of CelluTome™ + SOC (**Group 1A**; maximum of 3 CelluTome™ applications) versus 12 weeks of SOC (**Group 2B**) will be equal for both groups. Formally, $H_0: I_1 - I_2 = 0$; $H_A: I_1 - I_2 = D_1 \neq 0$, where I_1 is the incidence of AEs for **Group 1A** on a per subject basis, I_2 is same metric for **Group 2B**, D_1 is the difference ($I_1 - I_2$) assuming the alternative hypothesis, and statistical test used is the Mann-Whitney test.

H4: Correlation of wound area with protease activity at 4 weeks

The Pearson correlation coefficient (or Spearman's rho in the case of severe non-normality) calculated

from the mean change in wound area and protease activity between baseline and 4 weeks after 4 weeks of CelluTome™ + SOC (**Group 1A**) versus 4 weeks of SOC (**Group 2A**) will be equal for both groups. Formally, $H_0: r_1 - r_2 = 0$; $H_1: r_1 - r_2 = D_1 \neq 0$, where r_1 is the Pearson correlation coefficient for subjects in **Group 1A** calculated from difference in mean wound area and difference in mean protease activity between baseline and 4 weeks, r_2 is the same specified metric for subjects **Group 2A**, D_1 is the difference ($r_1 - r_2$) assuming the alternative hypothesis, and the statistical test used is Steiger's Z test with the assumption that r will have the same sign for both groups.

H5: Correlation of wound area with protease activity at 8 weeks

The Pearson correlation coefficient (or Spearman's rho in the case of severe non-normality) calculated from the mean change in wound area and protease activity between baseline and 8 weeks after 8 weeks of CelluTome™ + SOC (**Group 1A**) versus 8 weeks of SOC (**Group 2B**) will be equal for both groups. Formally, $H_0: r_1 - r_2 = 0$; $H_1: r_1 - r_2 = D_1 \neq 0$, where r_1 is the Pearson correlation coefficient for subjects in **Group 1A** calculated from difference in mean wound area and difference in mean protease activity between baseline and 8 weeks, r_2 is the same specified metric for subjects in **Group 2B**, D_1 is the difference ($r_1 - r_2$) assuming the alternative hypothesis, and the statistical test used is Steiger's Z test with the assumption that r will have the same sign for both groups.

H6: Reduction in pain score at 12 weeks

The change in mean pain score between baseline and at 12 weeks after 12 weeks of CelluTome™ + SOC (**Group 1A**) versus 12 weeks of SOC (**Group 2B**) will be equal for both groups. Formally, $H_0: \mu_1 - \mu_2 = 0$; $H_1: \mu_1 - \mu_2 = D_1 \neq 0$, where μ_1 is the mean difference in pain score for subjects in **Group 1A** between baseline and 12 weeks, μ_2 is the same specified metric in **Group 2B**, D_1 is the difference ($\mu_1 - \mu_2$) assuming the alternative hypothesis, and the statistical test used is the paired t test if data are normal and the Mann-Whitney test on a non-paired basis if data are non-normal.

H7: Proportion of wounds healed at 12 weeks (Groups 2B versus 2C)

The first hypothesis to be tested is that the proportion of wounds healed in **Group 2C** (12 weeks of SOC + 2 CelluTome™ applications) is no more than 15% lower than the proportion of wound healed in **Group 2B** (12 weeks of SOC). Noninferiority is established if the lower limit of the $(1 - 2\alpha) \times 100\%$ CI (confidence interval) for the difference (**Group 2C** – **Group 2B**) is above -15% where the equivalence margin, δ , is 15%. If non-inferiority is not established because the proportion of wounds healed in **Group 2C** is much higher than in **Group 2B**, the superiority hypothesis testing used in H2 will be utilized.

H8: Incidence of Adverse Events (AEs) (Groups 2B versus 2C)

The incidence of adverse events (AEs) by 12 weeks after 12 weeks of CelluTome™ + SOC (**Group 2C**; maximum of 2 CelluTome™ applications) versus 12 weeks of SOC (**Group 2B**) will be equal for both groups. Formally, $H_0: I_1 - I_2 = 0$; $H_A: I_1 - I_2 = D_1 \neq 0$, where I_1 is the incidence of AEs for **Group 2C** on a per subject basis, I_2 is same metric for **Group 2B**, D_1 is the difference ($I_1 - I_2$) assuming the alternative hypothesis, and statistical test used is the Mann-Whitney test.

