9.3 SAMPLE SIZE CALCULATIONS

A two-sided logrank test with an overall sample size of 225 subjects (113 in the control group and 112 in the treatment group) achieves 86.1% power at a 0.05 significance level to detect a hazard ratio of 1.74 when the proportion of wounds healed in the control group is 0.5. The study lasts for 12 weeks with all subjects beginning the study together (no accrual periods). The proportion dropping out of the control group is 0.033 per week. The proportion dropping out of the treatment group is 0.0083 per week. The proportion switching from the control group to another group with a hazard ratio equal to that of the treatment group is 0.

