9.7 STATISTICAL METHODS

MISSING DATA

Missing data may be the result of missed visits, subjects lost to follow-up or who have died, or data not available (e.g., smoking status).

Missing primary endpoint data within 12 weeks from start of study will not be imputed for ITT populations as these will constitute right-censored data in the time to heal analysis. The last visit for which data are available will constitute the start of censoring (healing outcome). For secondary endpoints within 12 weeks from start of study, the last observation carried forward (LOCF) principle will be used for ITT populations.

For adjusted analyses of primary and secondary endpoints, missing data for covariates used to adjust analyses may be imputed in separate models when the missing data for each covariate is $\leq 30\%$ and it can be reasonably demonstrated that the missing data for each covariate are MCAR.

FINAL ANALYSIS

Analysis can be started when database lock for the trial is initiated. In regard to statistical modeling, the initial list of independent variables will be examined for correlation between pairs. In the event that

correlation (however calculated) exceeds 0.7, a selection will be made between the 2 variables to avoid possible issues of co linearity and variance inflation.

The following analysis will be conducted:

1. Flow chart (subjects)
2. Overall trial statistics (enrollment dates, site numbers, numbers of subjects)
3. Demographics between groups at baseline (no statistical testing but identification of likely trial imbalances)
4. Count of subjects in each group
5. Primary endpoints within 6 and 12 weeks (time to heal; previously defined by groups) will be analyzed by Kaplan-Meier and log rank test (unadjusted); and then Cox regression to adjust for the following variables (with and without covariate imputation):

- Site
- Year enrolled (if trial lasts 2 years or more)
- Treatment group
- Initial area at randomization (cm²)
- Initial wound depth (cm)
- Age of wound at enrollment (days)
- Smoking status
- Prior VLU
- Pain score at randomization
- Patient age
- Gender
- Ethnicity/race
- VCS score
- Diabetes
- Patient on pain medications
- Smoking status
- BMI
- Infection episodes

6. Secondary endpoints will be analyzed as follows:

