- Proportion of wounds healed at 12 weeks will be analyzed by chi square (unadjusted); this endpoint may also be analyzed using logistic regression to adjust for the following variables (with and without covariate imputation) if needed:
 - Site
 - Year enrolled (if trial lasts 2 years or more)
 - Treatment group
 - Initial area at randomization (cm²)
 - Initial wound depth (cm)
 - Age of wound at enrollment (days)
 - Smoking status
 - Prior VLU
 - Pain score at randomization

- Patient age
- Gender
- Ethnicity/race
- VCS score
- Diabetes
- Patient on pain medications
- Smoking status
- BMI
- Infection episodes

Note: unadjusted testing for **Group 2C** versus **2B** will be non-inferiority, followed by superiority testing if the former fails and proportion of wounds healed in **Group 2C** is much higher than in **Group 2B**.

- A summary of the incidence of adverse events (count by patient):
 - AE (category)
 - SAE (category; brief description; resolution; should include death)
 - When event happened in relation to start of treatment (days)
 - Associated patient ID, site ID

Incidence of AEs will be analyzed by Mann-Whitney test on a per subject basis.

- Correlation of changes in wound area with changes in protease activity will be first analyzed by calculating the Pearson correlation coefficient for each group or Spearman's rho if data are grossly non-normal. For each subject the change in protease activity is calculated by subtraction of the value at 4 or 8 weeks from the value at baseline; reduction in wound area is calculated similarly. Differences in r will be analyzed using Steiger's Z test with the assumption that r will have the same sign for both groups. If significant differences are found between groups, further analysis using GLM doubly multivariate repeated measures (change in wound area and protease activity between baseline and 4 and 8 weeks) to adjust for the following variables (with and without covariate imputation) may be undertaken (ordinal re-categorization will be done if data are severely non-normal):
 - Site
 - Year enrolled (if trial lasts 2 years or more)
 - Treatment group
 - Initial area at randomization (cm²)
 - Initial wound depth (cm)
 - Age of wound at enrollment (days)
 - Smoking status
 - Prior VLU
 - Pain score at randomization
 - Patient age
 - Gender
 - Ethnicity/race
 - VCS score

CELLUTOME™ IN VENOUS LEG

- Diabetes
 - Patient on pain medications
 - Smoking status
 - BMI
 - Infection episodes

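### Sections 9.2 (H1) and 9.7 (item 5) conflict on whether the primary endpoint's Cox model depends on a significant log-rank result

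*Combined protocol and SAP*

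**What the plan says.** H1 compares time to heal between Group 1A and Group 2A at 6 weeks, and between Group 1A and Group 2B at 12 weeks. In both cases the "statistical test used is log rank applied to a Kaplan-Meier analysis". H1 then adds: "If either result is statistically significant, results will be adjusted using Cox regression and appropriate covariates".

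Section 9.7, item 5 of the final analysis, covers the same endpoints at the same two times. They "will be analyzed by Kaplan-Meier and log rank test (unadjusted); and then Cox regression to adjust for the following variables", followed by a named covariate list. No significance condition appears there.

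Elsewhere in 9.7 a condition is written out when one is meant. For the proportion healed, "this endpoint may also be analyzed using logistic regression to adjust for the following variables", if needed. For the protease correlation, "If significant differences are found between groups, further analysis using GLM doubly multivariate repeated measures" may be undertaken.

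Section 9.1.1 sets the level: unless specified otherwise, "all statistical testing will be two-sided and performed using a significance (alpha) level of 0.05". Section 9.3 states that the design "achieves 86.1% power at a 0.05 significance level to detect a hazard ratio of 1.74".

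**The concern.** The two sections give different rules for when the primary endpoint's Cox model is fitted, and the documents state no order of precedence. The choice could therefore be made after the log-rank p-values are known.

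The log-rank test yields a p-value and no effect size. The Cox model is the only planned analysis of time to heal that gives a hazard ratio with an interval. It is also the only primary analysis in which wound age, the stratification factor in section 9.4, is taken into account. If H1 governs, a trial in which neither log-rank test is significant reports none of this, although an interval is most needed then, to show which effects remain plausible. Whether covariate adjustment is done should not depend on the unadjusted p-value.

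**Working it through.** **Inputs.** From section 9.3: 113 control and 112 treatment subjects, hazard ratio 1.74, control healing 0.5 over 12 weeks with no accrual period, weekly dropout 0.033 (control) and 0.0083 (treatment), power 86.1%. From section 9.1.1: two-sided alpha 0.05. Exponential healing and dropout times are my assumption.

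**Step 1: reproduce the stated power.**
- Healing hazards per week: control ln 2 / 12 = 0.0578; treatment 1.74 × 0.0578 = 0.1005.
- Dropout hazards per week: control −ln(1 − 0.033) = 0.0336; treatment −ln(1 − 0.0083) = 0.0083.
- Expected healings = n × h/(h + c) × [1 − exp(−12(h + c))], with h the healing and c the dropout hazard. Control: 113 × 0.6325 × 0.6657 = 47.6. Treatment: 112 × 0.9234 × 0.7291 = 75.4. Total: about 123.
- Schoenfeld: Z = ln(1.74) × √123 / 2 = 3.07; power = Φ(3.07 − 1.96) = 86.7%.
- Freedman's formula gives 85.0% and a Lakatos-type calculation 85.7%. The stated 86.1% is reproduced.

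**Step 2: how often H1 would leave no adjusted hazard ratio.** The Cox model is withheld only if both tests miss significance, so P(neither) ≤ P(12-week test not significant) = 1 − 0.861 = 0.139, or at most about 14%. A simulation of 2,500 trials on the section 9.3 assumptions, with no prognostic covariate effect, gave a significant 12-week test in 86.0% and at least one significant test in 87.8%. About 12% of trials then have no adjusted estimate.

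**Step 3: the selection effect at the stated power.** With μ = 1.96 + z(0.861) = 1.96 + 1.085 = 3.045:
- E[Z | Z > 1.96] = μ + φ(1.96 − μ)/0.861 = 3.045 + 0.257 = 3.302.
- Ratio to μ: 3.302 / 3.045 = 1.084, so the log hazard ratio is about 8% too large.
- exp(1.084 × ln 1.74) = 1.82.

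In the same simulation, fitting Cox always gave a mean adjusted hazard ratio of about 1.74 at both times. Fitting it only when either test was significant gave 1.82 at 12 weeks and about 1.82 at 6 weeks.

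**Step 4: if the true effect is smaller.** These true values are assumptions. The other section 9.3 inputs are kept, with the 12-week test alone and the normal approximation:

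| True HR | Events | P(significant) | No adjusted HR, at most | Mean HR given significance |
|---|---|---|---|---|
| 1.74 | 123 | 0.867 | 13% | 1.82 |
| 1.5 | 117 | 0.593 | 41% | 1.69 |
| 1.3 | 111 | 0.283 | 72% | 1.63 |

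The first row is 13% and not 14% because it uses the Schoenfeld power of 86.7%.

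**Step 5: sensitivity to a prognostic covariate.** A covariate with log-hazard SD 0.7, a figure not in the documents, lowers the power of the unadjusted 12-week test to 72% at HR 1.74. The adjusted estimate is then missing in 24% of trials, and the conditional mean is 1.86 (12 weeks) and 1.88 (6 weeks). This does not break the 14% bound, which is conditional on the stated power.

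**The case against.** The strongest reply is that H1 says *if*, not *only if*. A plan that always fits the Cox model satisfies both sentences, and 9.7 is the more detailed list of what will be done. That stands as logic, so the conflict rests on the natural reading of H1. But the condition in H1 has no function if Cox is always fitted, and 9.7 writes out conditions for other endpoints when it intends them.

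Three stronger readings are tempting, and the documents do not support them.

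- *An adjusted estimate exists only for positive results.* The trigger is either result, so one significant test can lead to adjustment at both times. In the simulation without a covariate effect, about 24% of triggered trials at HR 1.74 had only one significant test. Testing is two-sided, so a significant result favouring control also triggers it.
- *The condition exaggerates the estimate.* In any given significant trial the Cox estimate is the same under H1 and 9.7, and deleting the condition shrinks none of them. The 8% is an average over trials that pass the filter. The fault is selective availability. It would also be wrong to carry HR 1.74 over to a much lower power, because that needs far fewer than the design's 123 or so events.
- *A null result would be uninterpretable.* Kaplan-Meier curves are produced under both rules, and the proportion healed at 12 weeks is analysed regardless. What is missing is the hazard ratio and its interval.

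**Conclusion.** The point holds as a conflict between 9.2 and 9.7 over when the primary endpoint's Cox model is fitted. Under H1 as naturally read, a trial with neither test significant has no adjusted hazard ratio or confidence interval. At the stated power and hazard ratio this is at most about 14% of trials, rising if the true effect is smaller. The reported estimates are a selected set, with an average log hazard ratio about 8% too large at the stated power, which is modest.

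These sizes rest on three assumptions:
- Significant means unadjusted p<0.05. H1 does not say whether the Hochberg adjustment at the end of 9.7 applies first; if it does, the trigger is stricter and the 14% bound need not hold.
- The section 9.3 model is taken at face value, with no allowance for the selection of Group 2B at week 6.
- In the closed-form calculation, the adjusted and unadjusted estimates behave alike.

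The log-rank test remains the decision test under both rules, so the primary conclusion and its type I error do not change. The correction is worth making because it removes results-dependent reporting of the only planned effect-size model for the primary endpoint.

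**What to change.** Delete the significance condition from H1. State in both 9.2 and 9.7 that the Cox model with the covariates named in 9.7 is fitted, and its hazard ratio with 95% CI reported, for the 6-week and the 12-week comparison whatever the log-rank result, and that the log-rank test remains the decision test. This also makes it unnecessary to define significant for this purpose.

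The cost is one deleted clause and a matching sentence in each section. No new data are needed, and 9.7 already plans the model. The change should be made before any comparison of the groups has been seen.
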